Cover Page

Title: What is the optimal stiffness and height of a running-specific leg prosthesis?

NCT #: N/A

Date of Document: 9/30/2014

PROTOCOL #: 13-2315

COMIRB Protocol

COLORADO MULTIPLE INSTITUTIONAL REVIEW BOARD [name] [contact] [contact]

Project Title: What is the optimal stiffness and height of a running-specific leg prosthesis?

Principal Investigator: [name].

I. Hypotheses and Specific Aims:

Our *primary objective* is to optimize prescription of **running-specific prostheses (RSP)** for Soldiers and Veterans with transtibial amputations by systematically varying RSP stiffness and height during running and sprinting.

Specific Aim 1: We aim to quantify the biomechanics (how someone moves), metabolic demands (how much energy is required to move), socket pressures (pressure within a prosthetic socket), and socket pistoning (axial displacement of the residual limb relative to the socket) of subjects with transtibial amputations using three brands (Ossur, Ottobock, and Freedom Innovations) of distance-running RSPs of different stiffness and height.

Hypothesis 1: The optimal stiffness and height distance-running RSP for each subject will minimize asymmetry and metabolic demand, without excessive socket pressure or socket pistoning.

Specific Aim 2: We aim to quantify the biomechanics, performance, socket pressures and socket pistoning of subjects with transtibial amputations using three brands (Ossur, Ottobock, and Freedom Innovations) of sprint-running RSPs of different stiffness and height.

Hypothesis 2: The optimal stiffness and height sprint-running RSP for each subject will minimize asymmetry and maximize top speed, without excessive socket pressure or socket pistoning.

II. Background and Significance:

Currently, there are no science-based objective methods for prescribing **running specific leg prostheses (RSPs)**. Thus, existing clinical practices waste time, money, and resources and do not necessarily optimize RSP prescription for Soldiers with leg amputations. Our **overall goal** is to develop a science-based method for optimal prescription of RSPs so that Soldiers and Veterans with leg amputations can regain the greatest possible level of functional ability and return to an active lifestyle and/or active duty.

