Day DR1: We will first vary the distance-running RSP stiffness (k) while keeping height (h) at the traditionally recommended level. Subjects will use an RSP with the manufacturer's recommended stiffness category based on their weight, an RSP that is one category softer (k-) and an RSP that is one category stiffer (k+) than the manufacturer's recommended stiffness. We will measure ground reaction forces, metabolic demand, socket pressures, and socket pistoning while subjects run at the speed required for their age/sex 50th percentile PFT (Physical Fitness Test) 2 mile run and at 3 m/s, a total of six trials. If the data warrant it, we may add an additional stiffness category to further fine tune the optimal stiffness. The optimal stiffness (k_{opt}) distance-running RSP will be the RSP that minimizes metabolic cost. This RSP stiffness will be used for Day DR2.

 $\underline{\text{Day DR2:}}$ We will keep RSP stiffness constant (k_{opt}) and vary the distance-running RSP height (h). Subjects will have used an RSP with an optimal stiffness (k_{opt}) at the recommended height (h_R) on day Day DR1. On Day DR2, they will also use and RSP with an optimal stiffness (k_{opt}) that is 2 cm shorter (h-), and 2 cm taller (h+). We will measure ground reaction forces, metabolic demand, socket pressures, and socket pistoning while they run at their PTF speed and at 3 m/s; a total of four trials. If the data warrant it, we may further fine tune RSP height in 1 cm increments. We will analyze the results of DR2 to identify the optimal height (h_{opt}) for each subject for one brand of a distance-running RSP.

Days DR3 and DR5: We will repeat the trials of Day DR1 and vary stiffness (k) for a different distance-running RSP brand. We will analyze the results of Days DR3 and DR5 to identify the optimal RSP stiffness (k_{opt}) to be used for Days DR4 and DR6.

Days DR4 and DR6: We will repeat the trials of Day DR2 and vary height (h) for a different distance-running RSP brand. We will analyze the results of Days DR4 and DR6 to identify the optimal height (hoot) for each subject using the respective brand of a distance-running RSP.

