Specific Aim 2. Subjects will complete six experimental sessions at the University of Colorado Locomotion Laboratory; each session on a separate day and requiring approximately two hours of time. During each experimental session, subjects will run and sprint over a range of speeds, from 3 m/s up to top speed on a force measuring treadmill while we measure their ground reaction forces, socket pressures, and socket pistoning. Subjects will run with three different brands (Ossur, Ottobock, and Freedom Innovations) of sprint-running RSPs with at least three different stiffnesses at one height and three different heights at one stiffness of each brand, a total of five or more different conditions per brand. Individual trials at each speed will be approximately 15-30 seconds long with at least 2 minutes rest between trials.

A safety harness attached to the ceiling above the treadmill and handrails beside the treadmill will be used during all running/sprinting trials to ensure subjects' safety. Each running trial will consist of at least 10 strides. To begin each trial, subjects will lower themselves from the handrails on to the moving treadmill belt. For each prosthetic stiffness and height condition, subjects will start a series of trials at 3 m/s, each subsequent trial will be incremented by 1 m/s until subjects approach their top speed, and then smaller speed increments will be employed until subjects reach their top speed. *Top speed* will be determined when subjects put forth maximal effort but cannot maintain their position on the treadmill for ten strides (Weyand, Sternlight, Bellizzi, & Wright, 2000). Subjects will be given as much time between trials as needed to recover fully (at least 2 minutes). At least seven trials will be performed by each subject for each prosthetic condition (e.g. 3, 4, 5, 6,

7, 7.3, 7.5 m/s) and a maximum of three series of trials will be performed each day. Our results will allow us to determine the optimal RSP mechanical stiffness (k_{opt}) and height (h_{opt}) for each person. The optimal sprint-running (SR) RSP will be the prosthesis that maximizes top speed.

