Day SR0: Subjects will be asked to give informed written consent and then will be fit and aligned by a certified prosthetist with three different sprint-running RSP brands, one from each company. We will measure each subject's height, weight, and limb segment lengths. Then, we will select an RSP stiffness category based on the subject's weight and manufacturer's recommendation. An appropriate RSP height for each subject will be chosen according to conventional practice. Our prosthetist will ensure that the prosthetic fit and alignment are adequate. Then, subjects will have time to accommodate to treadmill running and sprinting with each sprintrunning RSP over a range of speeds.

Day SR1: We will first vary the sprint-running RSP stiffness (k) while keeping height (h) at the recommended level. Subjects will use an RSP with the manufacturer's recommended stiffness category based on their weight, an RSP that is one category softer (k-) and an RSP that is one category stiffer (k+) than the manufacturer's recommended stiffness. We will measure ground reaction forces, top speed, socket pressures, and socket pistoning while subjects run and sprint over a range of speeds from 3 m/s up to their top speed. If the data warrant it, we may add an additional stiffness category to further fine tune the optimal stiffness. The optimal stiffness (k_{opt}) sprint-running RSP will be the RSP that maximizes top speed. This RSP stiffness will be used for Day SR2.

Day SR2: We will keep RSP stiffness constant (k_{opt}) and vary the sprint-running RSP height (h). Subjects will have used an RSP with an optimal stiffness (k_{opt}) at the recommended height (h_R) on day Day SR1. On Day SR2, they will also use and RSP with an optimal stiffness (k_{opt}) that is 2 cm shorter (h-), and 2 cm taller (h+). We will measure ground reaction forces, top speed, socket pressures, and socket pistoning while they run across a range of speeds from 3 m/s up to their top speed. If the data warrant it, we may further fine tune RSP height in 1 cm increments. We will analyze the results of SR2 to identify the optimal height (h_{opt}) for each subject for one brand of a sprint-running RSP

Days SR3 and SR5: We will repeat the trials of Day SR1 and vary stiffness (k) for a different sprint-running RSP brand. We will analyze the results of Days SR3 and SR5 to identify the optimal RSP stiffness (k_{opt}) to be used for Days SR4 and SR6.

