In Specific Aim 1, we propose to have subjects complete a total of six running trials per day and each trial will last 5 minutes. In Specific Aim 2, we propose to have subjects complete three sets of running and sprinting trials from 3 m/s up to top speed and each trial will last approximately 30 seconds. The proposed experimental trials may be too difficult, long, and/or exhausting. However, we have previously conducted up to eight running economy trials without detecting any effects of fatigue (Grabowski & Kram, 2008; Teunissen, Grabowski, & Kram, 2007). Moreover, our previous studies of Paralympic athletes with transtibial amputations suggest that subjects can complete three sets of running and sprinting trials from 3 m/s up to top speed without showing effects of fatigue (Grabowski et al., 2010). Thus, we believe that our proposed experimental protocol will be adequate; however if we do see signs of fatigue, we may need to spread out the protocol over more days.

We expect to find that for some subjects the optimal stiffness is either softer or stiffer than the manufacturer's recommended stiffness or that the optimal height is taller or shorter that the traditionally recommended height. Therefore, it may be necessary to add conditions to our protocol so that we can establish the true minimum metabolic cost or maximum speed. On Days 2, 4, and 6, we would be able to test an additional stiffness and height condition without exceeding the recommended number of trials per session. If additional trials are necessary, we may need to add an additional day to our protocol.

F. Data Analysis Plan:

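### The planned ANOVA compares average settings, so it does not test the claim in Hypotheses 1 and 2 about each subject's own optimal RSP

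*Combined protocol and SAP*

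**What the plan says.** **Hypotheses (section I).** Both are worded per subject. The optimal distance RSP "for each subject will minimize asymmetry and metabolic demand, without excessive socket pressure or socket pistoning". The optimal sprint RSP "for each subject will minimize asymmetry and maximize top speed, without excessive socket pressure or socket pistoning".

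**Selection rules (section IV.C).**
- Distance stiffness, Day DR1: "The optimal stiffness (k_{opt}) distance-running RSP will be the RSP that minimizes metabolic cost".
- Distance height, Day DR2: "We will analyze the results of DR2 to identify the optimal height (h_{opt}) for each subject for one brand". No criterion is given here. Section IV.E only suggests cost, where it speaks of adding conditions "so that we can establish the true minimum metabolic cost or maximum speed".
- Sprint, Specific Aim 2: "The optimal sprint-running (SR) RSP will be the prosthesis that maximizes top speed". Day SR1 repeats this for stiffness: "The optimal stiffness (k_{opt}) sprint-running RSP will be the RSP that maximizes top speed".

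**Analysis (opening paragraph of IV.C).** Subject and group averages are calculated for each condition. Each variable is then compared across all conditions by repeated-measures ANOVA with post-hoc tests at p < 0.05. Section IV.F, although titled as the data analysis plan, deals with records and data security and adds no statistical method.

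**Asymmetry and socket limits.** Leg symmetry is an outcome in IV.A, but the visible text defines no index for it. The list of analysed data in IV.C has possible components (leg stiffness, peak forces, stance and swing time) but no between-leg measure. The measurement section of IV.C sets the limits for excessive pressure and pistoning at 100 kPa and 8 cm.

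**Expected variation (IV.E).** The investigators expect that "for some subjects the optimal stiffness is either softer or stiffer than" the category recommended by the manufacturer, and say something similar for height.

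**The concern.** Choosing the optimum on one criterion and then asking whether symmetry follows is a coherent design; section III predicts that it will. But once cost or speed defines the optimum, lowest cost or highest speed at that optimum is no longer a finding. The part of each hypothesis that can be wrong is whether the chosen RSP is also that subject's least asymmetric one and stays within the socket limits.

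The planned ANOVA asks something else: whether the softer, recommended and stiffer settings differ on average over subjects. If subjects have different optima, the averages can be flat while the hypothesis holds in everyone. If one setting is more symmetric for everyone, the averages can differ clearly while the chosen optimum has nothing to do with symmetry.

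Subjects are to receive a recommendation of their optimal RSP (IV.D), and prescription algorithms are to follow (IV.G). The claim attached to that recommendation should be one that the stated analysis examines.

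**Working it through.** The plan gives no effect size, SD, power or sample-size basis, so there is no figure to reproduce. The check is a simulation under stated assumptions.

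**Inputs from the protocol.** Ten unilateral subjects per aim (IV.B); three stiffness settings per brand (IV.C); alpha 0.05 (IV.C).

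**Assumptions.** One brand; independent normal trial error with SD 1; each subject's own optimum is d SDs less asymmetric than the other two settings. The ANOVA F-test has 3 − 1 = 2 and (10 − 1)(3 − 1) = 18 degrees of freedom. 100,000 studies per case.

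**Why averaging hides the effect.** If a share p_j of subjects have their optimum at setting j, mean asymmetry there is a constant plus d(1 − p_j). With d = 2:
- shares of 1/3 each: 1.33, 1.33, 1.33 (no difference in means);
- 3/4/3: 1.4, 1.2, 1.4;
- 2/6/2: 1.6, 0.8, 1.6;
- 1/8/1: 1.8, 0.4, 1.8.

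The subjects' differing optima also enter the error term and enlarge it, which lowers rejection further.

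**Hypothesis true in every subject, d = 2**

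| Distribution of optima | ANOVA rejects |
|---|---|
| each setting equally likely | about 5% |
| exactly 3/4/3 | 0.2% |
| exactly 2/6/2 | 7% |
| exactly 1/8/1 | 59% |

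At d = 1 with equally likely optima the ANOVA rejects in 5%.

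**Hypothesis false.** One setting is 2 SDs less asymmetric for everyone and the cost optimum is random. The ANOVA rejects in 99.2%, while the optimum is the least asymmetric setting in 33% of subjects, the chance rate in this case.

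**A comparison at the subject's own optimum.** Paired t-test of asymmetry at the optimum against the mean of that subject's other two settings (equally likely optima; two-sided 5%, counted when in the right direction). In the study the optimum is chosen from noisy data, so the middle columns are the relevant ones. They assume that cost follows the same pattern with the same error SD.

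| d | Significant, chosen on noisy cost | Agreement, chosen on noisy cost | Significant, true optimum known | Agreement, true optimum known |
|---|---|---|---|---|
| 2 | 77% | 76% | 99.6% | 87% |
| 1 | 15% | 47% | 64% | 63% |

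Agreement is the share of subjects whose optimum is also observed as least asymmetric.

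**Chance agreement.** If the two optima are independent with shares p_j and q_j, expected agreement is Σ p_j q_j.
- Equal shares: 3 × (1/3)² = 33%.
- Both 20/60/20: 0.04 + 0.36 + 0.04 = 44%.
- Both 10/80/10: 0.01 + 0.64 + 0.01 = 66%.

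A fixed benchmark of 1/3 (or 1/5 over a brand's five base settings) would therefore mistake shared clustering for an individual link.

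**Precision.** Exact 95% intervals with ten subjects: 6/10 gives 26% to 88%; 7/10 gives 35% to 93%.

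**The case against.** **The study already has what it needs.** A reader might infer from the missing test that the study cannot say whether a named optimum is the least asymmetric setting or exceeds a socket limit. The documents do not support that. Subject averages per condition are planned, each leg's stiffness is calculated, and the 100 kPa and 8 cm limits give content to the word excessive in the hypotheses. For one subject these can be read off without an ANOVA. What is absent is a written step that does so at the chosen optimum and summarises it over subjects.

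**Symmetry may be covered.** A reader might also infer that symmetry was left out of the analysis. That goes too far: IV.A says leg symmetry will be derived from the measurements, the IV.C list need not be exhaustive, and Figure 2, said to show all outcomes, is not available here. The supported gap is that the visible text defines no index.

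**Selection may use more than cost.** It would be too strong to say that no choice of optimum uses asymmetry or a socket limit. Day DR2 names no criterion for distance height, and IV.E is only a general remark. The hypotheses could also be read as multi-criterion definitions of optimal. They would then conflict with the single-criterion rules for Days DR1 and SR1 and for Aim 2, and the ANOVA would still not examine them.

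**The rates are assumed.** This stands. IV.E says only that some subjects will depart from the recommended setting, which also fits 1/8/1, where the ANOVA rejects in 59%. The reasoning does not depend on the rates: a difference in average asymmetry is neither required by the per-subject claim nor enough to establish it.

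**Conclusion.** The point holds and should be fixed. The hypotheses concern each subject's own optimum; the only stated inference concerns condition averages; no written step compares a subject's chosen optimum with that subject's other settings. If the claim is true in every subject with a 2 SD benefit, the ANOVA rejects in about 5% of studies with equally likely optima, and in 0.2% to 59% across the fixed splits examined. If the claim is false because one setting suits everyone, it can reject in 99.2%. These figures rest on assumed effects, normal errors and one brand.

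Two limits apply. The ANOVA remains suitable for comparing average outcomes across settings, so the gap concerns Hypotheses 1 and 2 only. And the alternative is not powerful at this size: with the optimum chosen from equally noisy cost data, it is significant in about 77% of studies at 2 SDs and 15% at 1 SD. The 99.6% and 64% apply only if the true optimum were known, and should not be quoted as expected power.

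**What to change.** In section IV.C:

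(a) Name one between-leg symmetry index for the ten unilateral subjects in each aim, for example leg stiffness, in line with section III. Report bilateral subjects separately.

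(b) State that cost or speed defines the optimum and is not itself tested.

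(c) Prespecify a within-subject comparison of the index at each subject's chosen optimum against that subject's other settings, with subject as random effect, brand in the model, and setting as a fixed effect so that an average effect of a setting is not read as an individual link. (The simulated paired contrast does not include the setting adjustment.) Report per brand the proportion of subjects whose optimum is also the least asymmetric setting, with an exact 95% interval. Set it beside a chance rate taken from the observed distributions of the two optima, for example by permuting chosen optima across subjects, and not beside a fixed 1/3 or 1/5. Treat this as estimation.

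(d) Report for each chosen optimum whether it exceeds the protocol's own socket limits, or reconcile the socket clause of the hypotheses with the selection rules. No clinical rule is proposed.

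**Cost.** Some wording and a little more analysis of data already to be collected. The intervals will be wide, as shown above, so the result will describe agreement more than prove it.

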Specific Aim 1. We will recruit 15 runners; ten with unilateral and five with bilateral transtibial amputations that currently use and have at least one year of experience with distance-running RSPs. Subjects will be between 18-55 years old and have no current problems with their prosthesis or residual limb. There will be no restrictions on sex, race, or ethnicity for inclusion. Subjects will be at a K4 Medicare Functional Classification Level, which is defined as a person who has the ability or potential for prosthetic ambulation that exceeds basic ambulation skills, exhibiting high impact, stress, or energy levels. Subjects will have no known cardiovascular, pulmonary, or neurological disease or disorder. These inclusion/exclusion criteria will minimize any potential confounding variables, thereby increasing the internal validity of the proposed studies. Any person matching the inclusion criteria of the study, regardless of race or gender, will be recruited to participate.

Specific Aim 2. We will recruit 15 sprinters; ten with unilateral transtbial amputations and five with bilateral transtibial amputations that currently use and have at least one year of experience with sprint-running RSPs. Subjects will be between 18-55 years old and have no current problems with their prosthesis or residual limb. There will be no restrictions on sex, race, or ethnicity for inclusion. Subjects will be at a K4 Medicare Functional Classification Level, which is defined as a person who has the ability or potential for prosthetic ambulation that exceeds basic ambulation skills, exhibiting high impact, stress, or energy levels. Subjects will have no known cardiovascular, pulmonary, or neurological disease or disorder. These inclusion/exclusion criteria will minimize any potential confounding variables, thereby increasing the internal validity of the proposed studies. Any person matching the inclusion criteria of the study, regardless of race or gender, will be recruited to participate.

[figure not shown]

Figure 2. Overview of the experimental design. We will vary distance-running RSP (*Specific Aim 1*) and sprint-running RSP (*Specific Aim 2*) stiffness (k) and height (h) to create guidelines for prosthetic prescription.

C. Study Design and Research Methods

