The study will be a repeated-measures design. We will calculate subject and group averages for each condition from data normalized to a gait cycle. The data analyzed will include: leg stiffness, peak vertical and horizontal ground reaction forces, stance time, leg swing time, metabolic costs, top speed, peak socket pressure, and maximum socket motion. We will use repeated measures analysis of variance (ANOVA) to compare each variable across all conditions. Any significant differences will be further analyzed with either a Tukey HSD or Newman-Keuls follow-up procedure. In the case of an unequal number of subjects, we will use a Sheffe follow-up procedure. We will use p < 0.05 as a criterion for determining statistical significance. All statistical analyses will be performed with JMPIN software (JMPIN, SAS Institute, Cary, NC).

Specific Aim 1. Subjects will complete six experimental sessions at the University of Colorado Locomotion Lab; each session on a separate day and requiring approximately two hours of time. During each experimental session, subjects will run at two speeds, the speed required for their age/sex 50th percentile PFT (Physical Fitness Test) 2 mile run and a standard speed of 3 m/s on a force measuring treadmill while we measure their ground reaction forces, metabolic demand, socket pressures, and socket pistoning. Subjects will run with three different brands (Ossur,

Ottobock, and Freedom Innovations) of distance-running RSPs with three different stiffnesses at one height and three different heights at one stiffness of each brand, a total of five or more different conditions per brand at two speeds. Individual trials will be five minutes long with at least 2 minutes rest between trials.

Day DR0: Subjects will be asked to give informed written consent and then will be fit and aligned by a certified prosthetist with three different distance-running RSP brands, one from each company. We will measure each subject's height, weight, and limb segment lengths. Then, we will select an RSP stiffness category based on the subject's weight and manufacturer's recommendation. An appropriate RSP height for each subject will be chosen according to conventional practice. Our prosthetist will ensure that the prosthetic fit and alignment are adequate. Then, subjects will have time to accommodate to treadmill running with each distance-running RSP.

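### The planned ANOVA tests group means and counts differing optima as error, so it cannot show whether subjects' best stiffness differs, and each subject's k_opt carries no error estimate

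*Combined protocol and SAP*

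**What the plan says.** The target is individual. Hypotheses 1 and 2 (Section I) are worded for each subject. Section IV.C, Specific Aim 2, says the results will serve to "determine the optimal RSP mechanical stiffness (k_{opt}) and height (h_{opt}) for each person". Section IV.E adds: "We expect to find that for some subjects the optimal stiffness is either softer or stiffer than the manufacturer's recommended stiffness".

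The inference is about means. Section IV.C states: "We will calculate subject and group averages for each condition from data normalized to a gait cycle". It continues: "We will use repeated measures analysis of variance (ANOVA) to compare each variable across all conditions". Significant results go to Tukey HSD, Newman-Keuls or Scheffé comparisons, and "We will use p < 0.05 as a criterion for determining statistical significance". The model terms and the error term are not written out. No section names a subject-by-condition term, a random slope or a test of heterogeneity.

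The individual optimum is picked outside the ANOVA. On Day DR1 k_opt is the setting with the lowest metabolic cost; on Day SR1 it is the one with the highest top speed. No measure of error goes with the pick. It fixes the stiffness used on the next height day. Section IV.D promises each subject a recommendation, and Section IV.G plans prescription algorithms.

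**The concern.** With one value per subject and condition, a repeated-measures ANOVA divides the condition mean square by the subject x condition mean square. If some subjects do better softer and others stiffer, group means move towards each other and the real individual differences enlarge the denominator. What the study sets out to find is counted as noise.

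Two things are at stake. A non-significant ANOVA would not distinguish a stiffness that has no influence from one whose best value differs between people; a significant one would support a group difference and still be silent on individuals. And a spread of k_opt values would look like individual optima even if it were measurement error, with the recommendations and the algorithms resting on it.

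**Working it through.** **Inputs from the documents.** Aim 1: "We will recruit 15 runners; ten with unilateral and five with bilateral transtibial amputations". Aim 2: "We will recruit 15 sprinters; ten with unilateral transtbial amputations and five with bilateral transtibial amputations". So n = 15 in each. There are three stiffness categories (k-, recommended, k+) at one height in each of three brands; in Aim 1 the full set is "a total of five or more different conditions per brand at two speeds". Alpha is 0.05. The documents give no sample-size calculation, effect size or SD, so there is no planned figure to reproduce.

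**Assumptions.** Run-error SD = 1. Cost rises by d per category away from the subject's own optimum, with d = 0.5 or 1 error SD. Optima are the same in all three brands unless stated.

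**Tests.**
- Stiffness ANOVA: F = MS(stiffness) / MS(subject x stiffness), df 2 and (15 - 1)(3 - 1) = 28.
- Heterogeneity: F = MS(subject x stiffness) / MS(subject x stiffness x brand), df 28 and 28 x (3 - 1) = 56.

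**The mechanism by hand (d = 1).**
- Five subjects with their optimum at each category have costs (0, 1, 2), (1, 0, 1) and (2, 1, 0). Group means are (1, 2/3, 1), with squared deviations summing to 6/81.
- Expected MS(stiffness) = 1 + (3 x 15 x 6/81)/2 = 2.67.
- The interaction sums of squares per subject are 168/81, 24/81 and 168/81, so expected MS(subject x stiffness) = 1 + 3 x 5 x (360/81)/28 = 3.38. The denominator exceeds the numerator.
- If all 15 shared the recommended category, the costs (1, 0, 1) would give a numerator of 1 + (3 x 15 x 6/9)/2 = 16 over a denominator of 1.

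**Simulated rejection of the stiffness ANOVA.**

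| Optima over k-, recommended, k+ | d = 0.5 | d = 1 |
|---|---|---|
| Split in two, k- and k+ (fixed) | 0.7% | 0.0% |
| Exactly 5/5/5 | 3.0% | 0.7% |
| Random half k-, half k+ | 6% | 8% |
| Random thirds | 9% | 13% |
| 15/70/15% | 30% | 64% |
| 10/20/70% | 53% | 82% |
| 0/50/50% | 56% | 95% |

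With all optima at the recommended category, power at d = 1 was 99.7%; with no effect, rejection was about 5%. At 4,000 trials per scenario the Monte Carlo standard error is at most √(0.25/4,000) = 0.8 points.

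**Other cost shapes.** A one-brand version (20,000 trials; b = cost, in error SDs, of being one level off; b = 1 and 2) gave the same ordering:
- Step cost: 1.9% and 0.1% (exact 5/5/5), 5.0% and 5.2% (random thirds), 26% and 55% (10/20/70%).
- Quadratic cost: 5.6% and 0.7%, 24% and 26%, 90% and 95%, in the same order.

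**The pick.** With three settings, no true effect and equal error, each is best with probability 1/3, so 2/3 of picks fall away from the recommended category (66.7% simulated). Over 15 subjects x 3 brands = 45 picks, that is 30 by chance.

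**What the heterogeneity test adds.** It rejected in 58% and more than 99% of trials (d = 0.5 and 1) with the split in two, 42% and 99% with 5/5/5, and about 5% when all subjects shared one optimum with the same cost curve. Two limits matter:
- With all optima at k+ and only the steepness differing between subjects (0.2d or 1.8d), it rejected in 34% and 97%.
- With optima differing by subject within brand, it rejected in only 5% and 6%.

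**The case against.** A reader might infer that the ANOVA reports no effect whenever optima differ. The documents do not support that. It needs optima that balance around the recommended category, and Section IV.E says only that some subjects will differ from it, which is compatible with a common shift. Conditions are also coded relative to each subject's weight-based category, which may remove some of the heterogeneity. In the skewed cases above the ANOVA often rejects.

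A reader might also infer that a null ANOVA would overturn the individual optima or be reported as stiffness being unimportant. Neither is in the plan: the picks do not depend on the ANOVA, and no section says how a null would be read. Direct picking does not answer the point, however, because the pick has no error estimate.

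The model terms are unstated, so a factorial model with brand and speed could separate the interaction from residual error. That is possible, but the plan does not commit to it.

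The objections to the remedy stand in part. An interaction can reflect steepness and not location; metabolic power is computed in watts with no mass scaling stated, so heavier runners could show larger differences at the same optimum. The plan identifies optima per brand, so a null test would not prove a common optimum. For height, the recommended-height value is the selected best run from an earlier day, and k_opt may differ by brand, so those cells are not clean replicates. These limits shape the fix; they do not remove the gap.

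**Conclusion.** The concern holds in this form. The only planned inference tests group means, loses power when optima differ, and cannot show whether they differ; the individual picks cannot be told from noise as planned. ANOVA rejection is near or below 5% if optima balance exactly and 6% to 95% in the random or skewed three-brand cases. All these rates rest on the assumed d, error SD, cost shape and allocation of optima. The two-thirds figure needs only three settings with equal error and no true effect. That the ANOVA lacks a test of heterogeneity does not depend on the simulations. Severity is should-fix: the data needed are already planned.

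**What to change.** In Section IV.C, for metabolic cost (Aim 1) and top speed (Aim 2):

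1. Write out the model terms. Add a subject x stiffness component tested against subject x stiffness x brand (28 and 56 df with complete data), or a mixed model with random subject-by-stiffness effects. In Aim 1 include speed as a further factor.
2. Report the between-subject SD of the stiffness effect next to the group mean.
3. Give an uncertainty measure with each subject's k_opt.
4. Treat a supported component as evidence that the response to stiffness differs between subjects. Claim different optima only if the direction of the subject-level k- versus k+ contrasts also differs, consistently across brands. Do not take a null result as proof of a common optimum, since optima may be brand-specific.
5. Apply the same approach to height as exploratory only.

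The cost is a few lines of analysis text and code, with no new runs. The approach assumes that one-category offsets are roughly comparable across brands; the bench stiffness measurements planned in Section IV can be used to check this. The direction rule is conservative: it would not credit optima that differ only between neighbouring categories. The analysis may also show that individual optima are not supported.
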